5. AMENDMENTS AND UPDATES

None.

6. MILESTONES

Tab.1: Milestones of the study

Milestone	Planned date
Completion of feasibility assessment	31 January 2022
Start of data collection	1 October 2022
End of data collection	30 January 2023
Interim report 1 (after enrollment of 10% in Part 1 and 2)	31 October 2022
Final study report	15 April 2023

7. RATIONALE AND BACKGROUND

In clinical trials, patients are treated strictly according to a study protocol and show sometimes different risk factors, fewer comorbidities or a lower age than patients under standard care conditions. However, there is limited larger data collections on current therapy behavior in the 1L of patients with RCC, who are treated under standard care conditions in Germany.

The special interest of this retrospective Medical Chart Review project is to obtain in a Part 1 more precise data for the distribution of different 1L therapies of patients with aRCC, which have started within 01 January 2020 – 31 December 2021 and are representative for Germany. In Part 2 the effectiveness, sequences as well as the frequencies and handling of intolerabilities of combination therapies (ICI + TKI or ICI + ICI) in 1L aRCC will be analyzed by capturing data of patients, who completed a 1L in 01 January 2020 – 31 December 2021 with a follow up period of at least 3 months after completion. All data describe also the current therapy behavior and the resulting clinical effectiveness of the individual therapy protocols used in the 1L. These data allow the transferability of the results from clinical studies to standard care as well as the specific handling of intolerabilities. Particular emphasis is placed on analyses of this handling of intolerabilities during combination therapies with ICI + TKI or ICI + ICI. Information about current processes in decision findings regarding dose modifications or interruptions or interim / permanent discontinuations of one or both drugs can help to unify processes and to develop standard recommendations for daily care situations. Another point of the data analysis lies in the area of the medical disciplines and institutions that initiate and carry out 1L therapies for aRCC under standard care conditions. Questions about the different therapeutic behavior between urologists and medical oncologists, between practices and hospitals and between different regions in Germany are of particular relevance.

[figure not shown]
In conclusion, the rationale of this study is more clarity in the effectiveness of different 1L therapies, more clarity in the accordance of 1L therapies to national guidelines and more clarity in the handling of intolerabilities or other situations where dose modifications or discontinuation of treatment occurs

with combinations with ICI + TKI or ICI + ICI in the standard care settings of urologists and hematologists in practices and hospitals in Germany.

8. RESEARCH QUESTION AND OBJECTIVES

In Germany RCC is a rare cancer type with around 15.000 new diagnoses per year and an incidence of 15,7 per 100.000 for men and 7,5 per 100.000 for women (Robert Koch Institute, 2020). Regarding new incidences per year RCC is the 10th most common cancer type in women and 9th most common type in men, whereas the rate of mortality per year due to RCC was lower, 13th position in women with 1,8% and 13th position in men with 2,5% of all cancer-associated deaths (Robert Koch Institute, 2020). The mean age of onset in Germany is 72 years for women and 68 years for men. Risk factors for RCC are hereditary disease (ca. 5% of all cases with RCC) like von Hippel - Lindau – syndrome or Birt-Hogg-Dubé syndrome or acquired factors like obesity, chronic kidney failure, smoking or arterial hypertension, but also some professional exposition with halogenated hydrocarbons or long-term x-ray exposure (DGHO May 2022). Around 70-80% of the new RCC are diagnosed at an early stage and could be treated by partial or radical surgical resections in a curative intention. Most of the newly diagnosed patients were amendable for radical surgery, but 4.000 – 5.000 patients per year will start a new systemic therapy due to their advanced or metastatic disease. At present no neoadjuvant or adjuvant setting is established, but new data with TKIs and/or ICIs could be expected in the next few years. In stage I-IV (without metastases) the standard therapies are partial or radical nephrectomy (fig. 1).

Fig. 1: Guidelines for Renal Cell Carcinoma Stage I – IV (DGHO 2022 and German Cancer Society 2021)

[figure not shown]

In Stage IV with few number of resectable metastases, the partial or radical nephrectomy should be supplemented by metastatectomy of all metastases. Patients in stage IV without option for full resection of all metastases, a systemic anticancer therapy is recommended (fig. 1). Additionally, in selected patients with stage IV, a cytoreductive/palliative nephrectomy should be considered.

A part of patients with locally aRCC are not suitable for curative treatment by surgery. These patients would be treated like patients with metastatic diseases with systemic therapies under palliative intention.

In the guideline of the German Cancer Society ([S3-Leitlinie Nierenkarzinom, AWMF, Nov 2021](#)) and of the German Society for Hematology and Oncology ([DGHO, May 2022](#)) for these patients combinations of pembrolizumab or avelumab with axitinib or pembrolizumab + lenvatinib or nivolumab + cabozantinib are recommended as the preferred first-line therapy for all risk groups (fig.2). As an alternative for patients with intermediate and high risk, the combination of nivolumab plus ipilimumab could be used. In patients ineligible for ICI and a low risk rating bevacizumab + INF, pazopanib, sunitinib or tivozanib, with an intermediate and poor risk rating cabozantinib and sunitinib are recommended.

Fig. 2: Guidelines for Treatment of Stage IV Renal Cell Carcinoma (DGHO May 2022 and German Cancer Society Nov 2021)

For subsequent therapies in case of progression, relapse, no response or intolerable toxicities the recommended first choices for 2L are nivolumab or cabozantinib or lenvatinib + everolimus. As alternatives or second choices, axitinib or sunitinib or everolimus or pazopanib or sorafenib are listed.

In the pivotal studies the effectiveness for the combinations of ICI + TKI wwa shown with PFS ranges of 15,1 – 23,9 months, with OS rates at 12 months of 89,9 – 91% and with objective response rate (ORR) ranges of 51,4 – 71% ([Bini TI et al, 2019](#); [Motzer R et al, 2019](#), [Motzer R et al, 2021](#)).

In pivotal studies, a higher rate of modifications and discontinuations of one or both drugs were seen for combinations of ICI (pembrolizumab or avelumab) + axitinib. During the therapy with pembrolizumab + axitinib AEs of any cause led to discontinuation of either drug in 30.5%, discontinuation of both drugs in 10.7%, interruption of either drug in 69.9%, and dose reduction of axitinib in 20.3% of the patients in 1L line RCC of any risk ([Bini TI et al, 2019](#)). During the treatment with avelumab + axitinib 42% of the patients had at least one reduction in the dose of axitinib due to AEs and in 8% of the patients AEs led to a discontinuation of both avelumab and axitinib ([Motzer R et al, 2019](#)). In the pembrolizumab-plus-lenvatinib group, AEs of any grade led to discontinuation of lenvatinib, pembrolizumab, or both drugs in 37.2% of patients (lenvatinib, 25.6%; pembrolizumab, 28.7%; both drugs, 13.4%), to dose reduction of lenvatinib in 68.8% of patients and to interruption of lenvatinib, pembrolizumab, or both drugs in 78.4% of patients ([Motzer R et al, 2021](#)). A comparable situation could be found for combination of Nivolumab + Ipilimumab as also for this combination dose delays were described in up to 58% and discontinuations in up to 22% ([Motzer R et al, 2018](#)).

But the present handling of severe AEs in the standard care setting of combinations ICI + TKI or ICI + ICI in 1L RCC (e.g. dose reduction or interim discontinuation of axitinib or interim/permanent discontinuation of both drugs) seems to be unclear as no detailed data are available.

8.1. Primary Research Questions

Based on the above background, there are currently a number of unanswered questions for health services research:

- How is the effectiveness, defined as measurement of beneficial effects under “real world” clinical settings, (e.g. progression-free survival, overall survival and best response) of TKI and/or ICI as 1L in patients with aRCC?
- How are patients with aRCC treated in 1L under daily care conditions in Germany in general and in accordance to medical specialities (urology and medical oncology) and treatment settings (hospitals vs office-based practices)?
- Are all patients assigned to individual risk ratings under standard daily care conditions according to a scale developed by the IMDC before start of a 1L?
- How are patients treated in 1L in different risk rating groups and how is the adherence to national/international guidelines?
- What kind of previous and subsequent therapies are administered before and after 1L?
- How often are evaluations for PD-L1 expression performed before start of 1L and how many patients are positive (TPS $\geq 1\%$) or negative?

- How long are patients treated with TKI + ICI and ICI + ICI in 1L in general and in relation to specific therapies like avelumab + axitinib?
- How frequent are dose modifications and early discontinuations and what are the reasons?
- Are there differences in the handling of modifications among medical disciplines?

8.2. Study Objectives

To answer these questions the following objectives are derived:

Primary Objective(s):

- Progression-free survival (PFS) for 1L therapies, expressed as median and as rates at timepoints of 6, 9, 12 and 18 months after start of 1L

Secondary Objectives:

- Overall survival (OS) of 1L therapies, expressed as median and rates at timepoints of 12 and 18 months after start of 1L therapy
- Best response in 1L overall and in dependence of administered drug regimen
- Progression-free survival of 1L therapies in dependence of specific drug regimen
- Pre- and post-treatments (i.e. surgery, radiotherapy, medicinal therapies) before/after TKI + ICI and ICI + ICI in 1L
- Duration of response (DoR) in 1L overall and in dependence of administered drug regimen (TKI + ICI or ICI + ICI)
- Frequency of dose modifications and temporary/permanent discontinuations of 1L therapies and their reasons
- Proportions of modifications by dose reduction compared to cancelling single applications
- Effectiveness (PFS, OS and best response) of administered 1L therapies under real world conditions by medical specialty (urology, medical oncology) and setting (practice, hospital)

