- Supportive drugs prescribed during 1L
- Date of first response and best response in 1L incl. mode of assessment
- Assessment of first and best response in 1L
- Date of tumor progression
- Reasons for end of 1L
- Subsequent therapies (2L and higher) with drugs/protocol and dates for start / end
- Concomitant diseases and therapeutic medications

Data Sources	Source documents (paper or electronic medical charts) are those, in which patient data of daily care are recorded and documented in individual patient files. The data to be collected in the study will be obtained via a specific programmed eCRF. The data in the eCRF should be consistent with the relevant source documents. Medical records should contain demographic data, medical data, treatments and diagnostic documentations according to common practice. The documentation will be performed under full anonymization, so that a re-identification of single patients will not be possible. Based on this anonymization, queries for explanations or changes of data could not be submitted by the data management. All documented variables will be checked by data manager and/or medical lead of GermanOncology in relation to implausibility, inaccuracies or missing data. If implausibility or inaccuracies or missing data of single patients will be of great relevance for analyses, the data management and/or medical lead have the right to reject patients. For such rejected patients no payment will be triggered.

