9.2. Variables

The following variables will be captured by a specific eCRF and are needed for the analysis of all outcomes and for answering all research questions.

Tab. 2: List of all variables, role, data source and operational definitions

Variable	Role	Data source(s)	Operational definition
Age and gender	baseline characteristic	Medical Chart	Years; male/female
Weight and body surface	baseline characteristic	Medical Chart	kg, m ²
Date of first diagnosis	baseline tumor characteristic	Medical Chart	dd/mm/yyyy
Stage and risk rating (IMDC) at first diagnosis and at start of 1L	baseline tumor characteristic	Medical Chart	Favorable risk / intermediate risk / poor risk
Assessments and results of PD-L1 expression as TPS	baseline tumor characteristic	Medical Chart	y/n; 0-100%
Non-medicinal pre-treatments (primary OP, cytoreductive nephrectomy radiotherapy)	baseline tumor characteristic	Medical Chart	y/n; dd/mm/yyyy of OP; mode of OP; intention of OP (curative/palliative); period and dose of radiotherapy
Medicinal pre-treatments (adjuvant, neoadjuvant)	baseline tumor characteristic	Medical Chart	y/n; start/stop and used therapy protocol
Location of administration and performing medical discipline	Relevant for outcomes	Medical Chart	Urological practice; hematological practice; hospital with urological department; hospital with oncological department
Administered drugs / protocols in 1L	Relevant for outcomes	Medical Chart	administered therapy protocol
If applicable: Reason for ineligibility of ICI	Relevant for outcomes	Medical Chart	Concomitant disease; patient's wish
Duration of 1L	Relevant for outcomes	Medical Chart	Start/stop of therapy or every cycle;

Dates of administrations for i.v. drugs in 1L	Relevant for outcomes	Medical Chart	Dates of every administration
Dosages per administration	Relevant for outcomes	Medical Chart	Dose of administered drugs per administration
Dose modifications or drug administration cancelling or interim/permanent discontinuations of single drugs / complete therapy in 1L	Relevant for outcomes	Medical Chart	Each for single/all drugs: Dose modification; cancelling single administration; temporare discontinuation; permanent discontinuation
Reasons for modifications, cancelling of single administrations and discontinuations in 1L	Relevant for outcomes	Medical Chart	Each for single/all drugs: intolerance; age; performance status; patient's decision; other

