Supportive drugs prescribed during 1L	Relevant for outcomes	Medical Chart	Administered supportive drugs in connection with cancer therapy
Date of first response and best response in 1L incl. date and mode of assessment	Relevant for outcomes	Medical Chart	dd/mm/yyyy; CT/MRI/ultrasound/x-ray; clinical assessment; laboratory
Assessment of first and best response in 1L	Relevant for outcomes	Medical Chart	CR/PR/SD/PD/ND
Date of tumor progression	Relevant for outcomes	Medical Chart	dd/mm/yyyy
Reasons for end of 1L	Relevant for outcomes	Medical Chart	Progression; intolerance; decision oncologist; patient's wish; death; deterioration performance
Subsequent therapies (Second-line therapy (2L) and higher) with drugs/protocol and dates for start / end	Relevant for outcomes	Medical Chart	y/n; used drugs/regime; start/stop
Concomitant diseases and therapeutic measures	Relevant for outcomes	Medical Chart	Detailed diagnosis; therapeutic measures OP/medicinal/none/other

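### The objective on treatments before and after combination 1L includes surgery and radiotherapy, but no listed variable records either after 1L

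*Combined protocol and SAP*

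**What the plan says.** The secondary objective in section 8.2, repeated in the study information table and in the Abstract, reads "Pre- and post-treatments (i.e. surgery, radiotherapy, medicinal therapies) before/after TKI + ICI and ICI + ICI in 1L". Section 8.1 asks the matching research question, "What kind of previous and subsequent therapies are administered before and after 1L", also without limiting it to drugs.

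Section 9.2 introduces Tab. 2 as the variables "needed for the analysis of all outcomes and for answering all research questions". For the period before 1L, Tab. 2 has two rows:

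- "Non-medicinal pre-treatments (primary OP, cytoreductive nephrectomy radiotherapy" (surgery and radiotherapy), with the coding "y/n; dd/mm/yyyy of OP; mode of OP; intention of OP (curative/palliative); period and dose of radiotherapy".
- "Medicinal pre-treatments (adjuvant, neoadjuvant", with yes/no, start and stop, and the protocol used.

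For the period after 1L there is one treatment row, "Subsequent therapies (Second-line therapy (2L) and higher) with drugs/protocol and dates for start / end". It is coded as yes/no, drugs or regimen used, and start and stop. The Part 1 and Part 2 lists in the Abstract have the same single entry: "Subsequent therapies (2L and higher) with drugs/protocol and dates for start / end".

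**The concern.** The bracket in the objective defines what pre- and post-treatments are; it does not give examples. Non-drug treatment is specified in detail before 1L and not at all after it, so the variable list does not serve the objective that it is said to serve.

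At stake is the description of what follows TKI + ICI and ICI + ICI. Section 7 names treatment sequences as one purpose of Part 2, and Part 2 requires at least 3 months of follow-up after 1L is completed. From the listed variables, local treatment after 1L would go unreported, and a patient with local treatment only would look the same as a patient with no further treatment.

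**Working it through.** No sample size, error rate or event count bears on this point, and the plan gives no figure to reproduce. The check sets each component of the objective against the listed variables.

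Components in the objective: 3 kinds of treatment × 2 periods = 6.

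| Treatment | Before 1L | After 1L |
|---|---|---|
| Surgery | Listed (non-medicinal pre-treatments) | Not listed |
| Radiotherapy | Listed (non-medicinal pre-treatments) | Not listed |
| Medicinal | Listed (medicinal pre-treatments) | Listed (subsequent therapies) |

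Listed: 3 + 1 = 4 of 6. Not listed: 6 − 4 = 2 of 6, which is 2 of the 3 post-treatment components. The count is the same for Tab. 2 and for both lists in the Abstract.

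The next step is to see whether another entry could hold the missing data.

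- **Concomitant diseases (Tab. 2).** This row offers an operation as a therapeutic measure, but for concomitant diseases. It has no date and no radiotherapy option, and the Abstract describes the same item as medications.
- **Reasons for end of 1L (Tab. 2).** The options are progression, intolerance, physician's decision, patient's wish, death and worsening performance. None identifies local treatment.
- **Non-medicinal pre-treatments (Tab. 2).** The row has an operation date, but it is labelled as pre-treatment and given the role of a baseline tumour characteristic. It cannot be relied on to hold later procedures.
- **Free text (sections 9.5 and 9.7).** Entry is by pre-defined lists, with free text intended only after the choice of an other category in some fields. The coding of the subsequent-therapies row shows no such category.

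Last, can the data be obtained later? Section 9.3 says that, because of full anonymisation, data management cannot submit queries for explanations or changes. Section 9.6 lets a later SAP modify the analysis, but an SAP cannot supply data that were not collected.

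**The case against.** The strongest reply is that the eCRF is not among the documents. Section 9.5 says it is built to reconstruct the whole course of treatment from first diagnosis to the present, death or loss to follow-up. Section 9.1.1 asks that information on all treatments before, during and after 1L be available. Both show an intention to cover everything. This stands as far as it goes: the documents show that the field is not named, not that the eCRF lacks it. But neither passage defines a variable, and section 9.1.1 concerns what the chart holds rather than what is captured. If the eCRF does hold the field, Tab. 2 and the Abstract are incomplete and still need correcting.

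A second reply is that little depends on the gap. The outcome definitions in the Abstract include no measure of surgery or radiotherapy after 1L, and drug sequences are captured with regimen and dates. That is right, and it limits the point to part of one descriptive objective. Time to next treatment ends at the next therapy without saying whether local treatment counts, so the documents do not establish that this outcome is affected.

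Four stronger readings are tempting but not supported:

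- **Half of the objective is lost.** The count is two of six components.
- **Patients would be miscoded.** Under a row labelled for drug lines, a no for a patient with local treatment only is correct but incomplete. It would mislead only if a report presented it as no treatment of any kind, and nothing in the plan says so.
- **A given number of patients is affected.** No passage gives a rate of local treatment after 1L. Section 8 describes nephrectomy and removal of metastases as stage IV care without placing them after 1L, and where it describes treatment after progression it lists drugs only.
- **The data could never be recovered.** Section 9.5 provides for corrections with a history trail, so recovery is unlikely rather than impossible.

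**Conclusion.** The point holds as a mismatch between an objective and its variables. Two of the six treatment-by-period components, surgery after 1L and radiotherapy after 1L, cannot be reported from the variables as listed. The same gap appears in Tab. 2 and in both lists in the Abstract, and it applies to every patient documented. How many patients had such treatment is unknown, and the conclusion does not depend on that number.

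It rests on one assumption: that the eCRF follows the variable lists, which section 9.2 presents as sufficient for all research questions. The primary PFS objective, all pre-treatment components and drug therapy after 1L are not affected. The correction is worth making because it is cheap before data collection and hard to make afterwards.

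**What to change.** Before data collection starts (planned for 1 October 2022; the protocol is dated 19 August 2022), add a variable such as *Non-medicinal post-treatments (surgery, radiotherapy) after 1L* to Tab. 2, to both variable lists in the Abstract and to the eCRF. Code it like the pre-treatment row: yes/no; date, mode and intention of the operation; period and dose of radiotherapy. Keep it to the period after 1L, since the objective speaks of before and after, not during. In the report, show local treatment only separately from no further treatment.

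The cost is one eCRF block mirrored from an existing one and slightly more documentation per chart. The sample size does not change.

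If the field is not added, restrict the post-treatment part of the objective to medicinal therapies wherever it appears (study information table, Abstract, section 8.2) and say so. That costs no data collection, but it gives up the description of local treatment after combination 1L.

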9. RESEARCH METHODS

The present 1L treatment of patients with aRCC in Germany is wide-ranging with several options like combinations of ICI + TKI, ICI + ICI or monotherapies with TKI alone. Some of these therapies are only recommended in specific risk situations or in cases of ineligibilities for ICI, but at present there is only limited information available about decisions in 1L aRCC. Additionally, a higher proportion of patients with combined therapies of ICI + TKI or ICI + ICI show intolerabilities with the necessary for dose modifications or interim / permanent discontinuations of one or both drugs, but the processes of decision finding between dose modifications, interruptions and discontinuation are also unclear, although these processes would be very important for the outcomes of the therapy. In contrast to study protocols with clear specifications for handling AEs, in standard daily care the decision processes seem to be in the discretion of every oncologist. But at present, no detailed information about these

processes in standard daily care are available. Such information is also important as these therapies could be administered under in- or out-patient's settings and by urologists or medical oncologists.
Study design

The general design of this data project is a sampling of data about patients with aRCC receiving a 1L therapy, with a start (part 1) or completion (part 2) in 01 January 2020 – 31 December 2021. Data will be documented retrospectively and under full anonymization by investigators or their designees in a specific eCRF. All analyses and reports will be performed under aggregation of data as secondary data reports.

